5.7.2.1 Administration Related Reactions

Signs and symptoms associated with administration related reactions will be listed and summarized by previous randomization and overall. The number of patients that

experienced administration related reactions will be summarized by administrated dose level at each visit.

5.7.2.2 CNS Symptoms Temporally Associated with ARIA-E MRI Findings

In this report, symptomatic ARIA-E is defined as onset or worsening of CNS symptom(s) that is/are temporally associated with ARIA-E MRI findings. A programmatic approach to capture symptomatic ARIA-E will be adopted in the analysis, since CNS symptoms have not been consistently captured in the CRF AE form. For programmatic retrieval, CNS symptoms temporally associated with ARIA-E MRI findings were defined as all AEs from the Nervous System Disorders and Psychiatric Disorders SOCs that had onset between 4 weeks prior to ARIA-E onset through ARIA-E resolution, and not falling under ARIA-associated PTs.

The list of ARIA-associated PTs include:

- Amyloid related imaging abnormalities
- Amyloid related imaging abnormality-microhaemorrhages and haemosiderin deposits
- Amyloid related imaging abnormality-oedema/effusion
- Cerebral amyloid angiopathy
- Brain oedema
- Vasogenic cerebral oedema
- Brain stem microhaemorrhage
- Cerebellar microhaemorrhage
- Cerebral microhaemorrhage
- Cerebral haemosiderin deposition
- Magnetic resonance imaging head abnormal
- Superficial siderosis of central nervous system

The CNS symptoms temporally associated with ARIA-E MRI findings (programmatic retrieval) will be listed and summarized by previous randomization and APOE ϵ 4 genotype, and overall. A listing of AE reported as Symptoms of ARIA-E (eCRF) will be provided as well.

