ARIA events were manageable and were time-, dose-, and APOE ϵ 4 status-dependent. Incidences of ARIA-E by treatment arm were 2 (0.8%) in placebo, 18 (6.6%) in the 105-mg gantenerumab, and 32 (12.3%) in the 225-mg gantenerumab groups. For ARIA-H, the incidence was 29 (10.9%) in placebo and 52 (19.2%) and 34 (13.1%) in the 105 and 225 mg gantenerumab treatment arms, respectively. The rates of new ARIA-E were highest between 3 and 6 months of treatment (3.4% and 7.5% as compared to 0.9% and 0.5% between 9 and 12 months of treatment, in the 105- and 225-mg gantenerumab groups, respectively) and decreased substantially after the first year of treatment. Significantly, ARIA-E did not recur in subjects who restarted treatment at half of the original dose. Most ARIA events were asymptomatic (~90%), non-serious, of mild severity, had an MRI Barkhof Grand Total score (BGTS) median score of 3, with only 10% of ARIA-E scoring >10, and did not lead to more serious consequences. With respect to APOE ϵ 4 status, WN25203 data are consistent with other anti-fibrillar A β data showing an increased rate of ARIA incidence for APOE ϵ 4 carriers versus non-carriers (Salloway et al. 2014; Sperling et al. 2012b).

The overall incidence of injection site reactions was 15.4% with majority of the events of mild intensity. Incidence of injection site reactions by treatment arm was 4.5%, 18.8%, and 23.1% in the placebo, 105-mg gantenerumab, and 225-mg gantenerumab groups, respectively.

In Study WN25203, gantenerumab was safe and well tolerated, with an overall adverse event profile consistent with previous studies and expected findings in an elderly population.

Please refer to the Gantenerumab IB for *more detailed safety data from gantenerumab clinical studies*.

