5.7.3 Magnetic Resonance Imaging Safety Findings

The MRI safety findings will be analyzed only on the safety population with post-OLE baseline MRI. The incidence and severity of ARIA-E and ARIA-H will be summarized by APOE ϵ 4 genotype and up-titration and overall at each dose level. Recurrence of ARIA-E will be summarized by previous randomization and overall. Other ARIA-E characteristics will be summarized by previous randomization and APOE ϵ 4 genotype and overall, and by up-titration scheme and overall. Same for other ARIA-H

characteristics as well. ARIA-E with CNS symptoms will be summarized by previous randomization and APOE ε4 genotype and overall.

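### OLE SAP 5.7.2.2 counts coincidental nervous-system and psychiatric AEs as symptomatic ARIA-E, and no background rate is planned to show how many

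*SAP*

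**What the plan says.** The OLE SAP, section 5.7.2.2, first gives the concept: "symptomatic ARIA-E is defined as onset or worsening of CNS symptom(s) that is/are temporally associated with ARIA-E MRI findings". It uses a programmatic rule "since CNS symptoms have not been consistently captured in the CRF AE form".

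The rule has two parts:

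- **Which AEs count:** "CNS symptoms temporally associated with ARIA-E MRI findings were defined as all AEs from the Nervous System Disorders and Psychiatric Disorders SOCs". The section lists 12 excluded preferred terms. It has no list of symptom terms and no causality or severity criterion.
- **When they count:** AEs "that had onset between 4 weeks prior to ARIA-E onset through ARIA-E resolution, and not falling under ARIA-associated PTs". No maximum length is set, and the section does not say where the window ends if ARIA-E has not resolved.

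The retrieved events are listed and summarized by previous randomization, APOE ε4 genotype and overall. Section 5.7.3 repeats this for the MRI safety findings: "ARIA-E with CNS symptoms will be summarized by previous randomization", by genotype and overall. The investigator-attributed source is handled differently: "A listing of AE reported as Symptoms of ARIA-E (eCRF) will be provided as well".

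Section 5.7.2 plans AE and SAE rates per patient-year, with total OLE treatment time as the denominator. No section plans the rate of this particular set of AEs inside and outside ARIA-E windows, or in patients without ARIA-E.

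**The concern.** The inputs to the label are an AE's onset date, its SOC and preferred term, and the two ARIA-E dates. None of these separates a symptom of ARIA-E from an AE that would have happened anyway. With any background rate above zero, some ARIA-E will be labelled by coincidence. The window is four weeks plus the duration of the ARIA-E, so this happens more often when ARIA-E lasts longer.

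Safety and tolerability are the primary objective of the OLE, and ARIA is an identified risk. Protocol 1.4.8 relies on ARIA being mostly asymptomatic in its benefit-risk summary, so a reader will turn to this table for the symptomatic share. As planned, nothing beside the table shows how much of that share background AEs could explain.

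**Working it through.** **The documents' own figure.** Protocol 1.3.3 says of Study WN25203: "Most ARIA events were asymptomatic (~90%), non-serious, of mild severity". This cannot be reproduced, because no symptomatic count is given. The ARIA-E incidences in the same section do reproduce: 2/266 = 0.75% (stated 0.8%), 18/271 = 6.64% (6.6%) and 32/260 = 12.31% (12.3%).

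**Inputs.**

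- Window W = 4 weeks + ARIA-E duration (OLE SAP 5.7.2.2).
- Duration is not in the documents. Protocol 5.1.4.2 puts follow-up scans about a month apart, so the shortest duration likely to be observed is about 4 weeks, giving W = 8. I assume 4 to 24 weeks, so W = 8 to 28.
- The background onset rate r of non-excluded AEs in the two SOCs is not in the documents. I assume 0.1 to 1.0 per patient-year.

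**Formula.** For a patient with one ARIA-E episode and AEs arising independently of it, the chance of a label is 1 - exp(-r × W / 52.18). For example, with r = 0.5 and W = 16, r × W / 52.18 = 0.153 and the chance is 14.2%.

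| Window (weeks) | r = 0.1 | r = 0.3 | r = 0.5 | r = 1.0 | Rate at which chance labels 10% |
|---|---|---|---|---|---|
| 8 | 1.5% | 4.5% | 7.4% | 14.2% | 0.69 |
| 12 | 2.3% | 6.7% | 10.9% | 20.5% | 0.46 |
| 16 | 3.0% | 8.8% | 14.2% | 26.4% | 0.34 |
| 20 | 3.8% | 10.9% | 17.4% | 31.8% | 0.28 |
| 28 | 5.2% | 14.9% | 23.5% | 41.5% | 0.20 |

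The last column is -ln(0.9) × 52.18 / W = 5.498 / W per patient-year.

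**Sensitivity to uneven rates between patients.** With gamma-distributed patient rates of variance 1 (relative to the mean), the chance is 1 - 1/(1 + r × W / 52.18). The 10% thresholds become 0.73, 0.48, 0.36, 0.29 and 0.21. The largest cell falls from 41.5% to 34.9%. The pattern is unchanged.

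**Effect of duration.** At r = 0.5, lengthening the window from 8 to 28 weeks raises the chance label from 7.4% to 23.5% with no causal effect at all.

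**Mixing with real symptoms.** As an illustration, if 10% of ARIA-E were truly symptomatic and background labelled 10% independently, the table would show 1 - 0.9 × 0.9 = 19%.

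**Features that move the background.** Protocol 5.3.5.10 keeps events clearly due to expected AD progression out of the AE data, which lowers r. In the other direction, Protocol 5.2.4 has patients asked about CNS AEs before each MRI, and Protocol 5.1.4.2 makes MRI roughly monthly while ARIA-E is followed. CNS AEs are therefore ascertained more often inside the window than outside it.

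**The case against.** The best defence is that the rule is openly a temporal one. The section title says so, no causal claim is made, the analysis is descriptive and the OLE has no hypotheses. Where CRF capture was inconsistent, a broad retrieval that over-counts possible harm is a reasonable choice. The retrieved events and the eCRF-attributed symptoms are both listed, and overall AE rates per patient-year are planned. All of this stands, and it is why the retrieval should be kept. It does not supply the missing reference: the planned rates are not split by ARIA-E window, and a listing gives no share to compare.

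Three stronger readings are tempting, and the documents do not support them:

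- **That the window is open-ended.** It closes at resolution. It is uncapped and of variable length.
- **That unrelated AEs alone will match or exceed the roughly 10% symptomatic share seen before.** This needs a background of about 0.20 to 0.69 per patient-year, depending on the window, and no document gives one. At 0.1 the chance share stays at 1.5-5%. The earlier figure is also for ARIA events in general, in a prodromal AD study at 105 and 225 mg, with no statement of how symptoms were attributed. It is not a like-for-like benchmark.
- **That differences between groups in the table reflect ARIA-E duration.** They would if durations differ between groups, but the documents do not show that they do.

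There is also a fair objection to the obvious remedy. Because CNS AEs are sought more often inside the window, and can themselves prompt an unscheduled MRI (Protocol 4.5.13), a ratio of inside to outside rates can exceed 1 without causation. This limits how the ratio may be read. It does not remove the need for the rates.

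**Conclusion.** The concern holds as a gap in the planned presentation. The programmatic label counts coincidental AEs, counts more of them the longer ARIA-E lasts, and is reported with no reference rate. The resulting overstatement cannot be sized from the documents. On the assumptions above it is 1.5-5% of ARIA-E patients at 0.1 AEs per patient-year, 7-24% at 0.5 and 14-42% at 1.0, for windows of 8 to 28 weeks. These figures assume one episode per patient and AEs independent of ARIA-E. They ignore the heavier ascertainment inside the window, which would add to them. Symptoms never recorded as AEs would be missed by this rule too, and that works the other way. The point justifies an inexpensive addition. It does not justify dropping the retrieval or treating the table as invalid.

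**What to change.** Keep the retrieval in 5.7.2.2 and add the following:

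1. The rate per patient-year, with 95% CI, of the same AEs (same SOCs, same excluded terms) in three places: inside the ARIA-E window; in the remaining OLE time of patients with ARIA-E; and in patients without ARIA-E, by APOE status and previous randomization. State where the window ends when ARIA-E is unresolved, since the denominator depends on it.
2. The share expected from background beside the observed share. This can be computed by applying the ARIA-E-free rate to each actual window with the formula above and averaging.
3. A summary, not only a listing, of the eCRF-attributed symptoms of ARIA-E.
4. Wording that calls the programmatic result 'temporally associated' throughout and does not read it as causal. It should say that CNS AEs are ascertained more often inside the window, so a rate ratio above 1 is not by itself evidence of causation and should not be the sole basis for statements on symptomatic ARIA-E.

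The cost is essentially one extra table from AE and MRI data already collected, plus SAP wording. Estimates will be imprecise in the small genotype groups.

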5.7.3 Magnetic Resonance Imaging Safety Findings

The MRI safety findings will be analyzed only on the safety population with post-OLE baseline MRI. The incidence and severity of ARIA-E and ARIA-H will be summarized by APOE ϵ 4 genotype and up-titration and overall at each dose level. Recurrence of ARIA-E will be summarized by previous randomization and overall. Other ARIA-E characteristics will be summarized by previous randomization and APOE ϵ 4 genotype and overall, and by up-titration scheme and overall. Same for other ARIA-H

characteristics as well. ARIA-E with CNS symptoms will be summarized by previous randomization and APOE ε4 genotype and overall.

5.7.4 Laboratory Data

Laboratory data will be summarized by previous randomization and overall for each assessment visit using descriptive statistics of absolute values, change from baseline values, and percentage change from baseline. The proportion of patients who develop marked abnormalities during study treatment, on the basis of the National Cancer Institute Common Terminology Criteria for Adverse Events Version 4.0 (NCI CTCAE v4.0) and the International Standard for Handling and Reporting of Laboratory Data (COG 2.2), will be summarized.

5.7.5 Vital Signs

Vital signs assessments include systolic blood pressure, diastolic blood pressure, and pulse measured throughout the study. Summaries of vital sign measurements by previous randomization and overall at each assessment visit using descriptive statistics will be generated for the actual values, the change from baseline, and the percentage change from baseline.

5.7.6 Electrocardiograms

ECGs were collected throughout the study. Descriptive statistics will be generated by previous randomization and overall at each assessment visit for the actual values, the change from baseline and the percentage change from baseline for the following parameters:

- Heart rate
- PQ (PR) interval
- QRS interval
- QT interval
- RR interval
- QT corrected using Bazett's formula (QTcB) and QT corrected using Fridericia's formula (QTcF).

Duration of the QT interval is inversely correlated with the corresponding heart rate, so it should be corrected relative to heart rate to allow a reliable interpretation of changes in the QTc interval, independent of the changes in the heart rate. The QT intervals will be corrected for the heart rate using Bazett's and Fridericia's as follows:

- The QTcB value will be calculated as the QT interval (in milliseconds) divided by the squared root of the RR interval (in seconds).
- The QTcF value will be calculated as the QT interval (in milliseconds) divided by the cube root of the RR interval (in seconds).

QT/QTc outliers will be categorized as recommended in the E14 guidance. In some cases, multiple ECGs were performed in error. In these cases, the mean values across the ECGs should be used.

Abnormal ECG measurements will be summarized by previous randomization and overall at each assessment visit.

5.7.7 Columbia–Suicide Severity Rating Scale

The C-SSRS (<http://www.cssrs.columbia.edu>) is an assessment tool used to assess the lifetime suicidality of a patient (C-SSRS at baseline) as well as any new instances of suicidality (C-SSRS since last visit). The structured interview prompts recollection of suicidal ideation, including the intensity of the ideation, behavior, and attempts with actual/potential lethality. During the OLE, the C-SSRS will be collected every 6 months. Additional C-SSRS may be collected as deemed necessary by the Principal Investigator.

Suicidal ideation, suicidal behavior, and self-injurious behavior without suicidal intent will be summarized by previous randomization and overall at each assessment visit.

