4.5.6.6 Columbia–Suicide Severity Rating Scale

The C-SSRS (<http://www.cssrs.columbia.edu>) is an assessment tool used to assess the lifetime suicidality of a patient (C-SSRS at baseline) as well as any new instances of suicidality (C-SSRS since last visit). The structured interview prompts recollection of suicidal ideation, including the intensity of the ideation, behavior, and attempts with actual/potential lethality. The C-SSRS baseline will be collected at baseline and the C-SSRS since last visit will be collected at subsequent visits.

The C-SSRS will be conducted at visits, as indicated in the schedule of assessments. The assessment will be completed by a certified C-SSRS rater after interviewing the patient and the patient's caregiver when in attendance at the visit.

During the OLE, the C-SSRS will be collected every 6 months. Additional C-SSRS may be collected as deemed necessary by the Principal Investigator.

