Appendix 2 OLE Schedule of Assessments Part 2: Years 1 and 2 (cont.)

Table 1: Patients Previously on 225 mg Gantenerumab: Carriers (cont.)

- ^l At all visits when a PK and ADA samples (including PK obtained for ARIA findings) are needed, the samples should be obtained just before administration of gantenerumab, unless at weeks 53 and 101. Accurate recording of the time of study drug administration and PK sampling is critical.
- ^m Females of childbearing potential (including those who have had a tubal ligation) must have a urine pregnancy test performed at the site prior to each dose administration. If a urine pregnancy test is positive, it must be confirmed by a serum pregnancy test at the central laboratory.
- ⁿ Lumbar puncture at Weeks 52 and 104 are optional. Lumbar puncture must be performed in the morning (between 8:00 a.m. and 12:00 p.m.) to minimize potential diurnal variation of CSF parameters. Lumbar puncture should be performed 10–20 days after dosing.
- ^o From Weeks 56–100, C-SSRS should only be obtained at week 72. C-SSRS may be obtained at any time deemed necessary by the investigator.
- ^p Patients participating in the PET substudies and whose last PET was more than 9 months ago will need a pre-OLE PET scan prior to starting the OLE.
- ^q Physical and Neurologic Exam prior to OLE is optional.

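### The open-label extension C-SSRS summary is by visit only, so it cannot show how many patients had any or new suicidality, and unscheduled assessments have no defined place in it

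*SAP*

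**What the plan says.** The OLE SAP (the second plan in the SAP file) lists C-SSRS suicidality among the safety outcomes in 1.1.2.4, and 1.1.1 makes safety and tolerability the primary objective of the OLE. The only C-SSRS analysis is in 5.7.7: "Suicidal ideation, suicidal behavior, and self-injurious behavior without suicidal intent will be summarized by previous randomization and overall at each assessment visit".

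Three features of data collection matter:

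- **Recall.** Protocol 4.5.6.6: "The C-SSRS baseline will be collected at baseline and the C-SSRS since last visit will be collected at subsequent visits".
- **Frequency.** OLE SAP 5.7.7: "During the OLE, the C-SSRS will be collected every 6 months". Protocol Appendix 2 (Tables 1 to 4) marks Open-Label Day 1 and Weeks 24, 48 and 104, and a footnote adds: "From Weeks 56–100, C-SSRS should only be obtained at week 72". Table 5 then marks +24 and +52 weeks in each additional year, and Follow-Up 1.
- **Extra assessments.** OLE SAP 5.7.7: "Additional C-SSRS may be collected as deemed necessary by the Principal Investigator". Appendix 2 says the same ("C-SSRS may be obtained at any time deemed necessary by the investigator") and marks the C-SSRS in the unscheduled-visit column.

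Protocol 6.1.4, which 6.2 applies to Part 2, adds only changes in C-SSRS scores from baseline over time. The OLE SAP states that it supersedes the protocol.

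**The concern.** The question a safety reader asks is how many OLE patients had any suicidal ideation, behaviour or self-injury after starting open-label dosing, and in how many of them it was new. A visit-by-visit table does not answer it. The same patient may sit in several rows, and nothing in 5.7.7 separates a new finding from one already present before the OLE.

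An assessment that an investigator adds because of a worry is plausibly among those most likely to be positive, yet no rule assigns it to a row. Because later forms ask only about the time since the last visit, the next scheduled form need not report the same event. What is at stake is a listed safety outcome, under the primary objective of the OLE, that cannot be read off the planned output.

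**Working it through.** **1. No figure to reproduce.** The documents give no expected rate, event count or precision for OLE suicidality. The numbers below are illustrations with stated assumptions.

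**2. Do the rows determine the number of patients?** Inputs: N = 230 patients entered the OLE (OLE SAP, Introduction). There are k = 4 scheduled post-baseline rows in the first two years (Weeks 24, 48, 72, 104), and k = 4 + 2 × 3 = 10 if a patient stays for three additional years. Assume x positive patients in every row and no missing forms. The number ever positive is at least x (the same patients each time) and at most min(k·x, N) (different patients each time).

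| x per row | Row % (x/230) | k = 4: patients ever positive | k = 10: patients ever positive |
|---|---|---|---|
| 1 | 0.4% | 1 to 4 (0.4% to 1.7%) | 1 to 10 (0.4% to 4.3%) |
| 2 | 0.9% | 2 to 8 (0.9% to 3.5%) | 2 to 20 (0.9% to 8.7%) |
| 5 | 2.2% | 5 to 20 (2.2% to 8.7%) | 5 to 50 (2.2% to 21.7%) |

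Identical rows are compatible with a four-fold range over two years and a ten-fold range over five. Events found only at unscheduled forms would come on top.

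**3. Unscheduled forms.** Section 5.7.7 permits them. The OLE SAP has no visit-windowing rule; the rule in section 4.4 of the Part 1 SAP covers Part 1 efficacy only. Section 5.7.7 does not promise a listing, whereas 5.7.2 (adverse events), 5.7.2.1 (administration reactions), 5.7.2.2 (CNS symptoms with ARIA-E) and 5.7.8 (deaths) do. Suppose an extra form is completed at Week 36. The Week 48 form then looks back 48 − 36 = 12 weeks, so an event reported at Week 36 need not appear at Week 48.

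**4. Look-back length, if the last visit means the last C-SSRS.** Differences between consecutive scheduled weeks:

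- Week 24: 24 − 0 = 24
- Week 48: 48 − 24 = 24
- Week 72: 72 − 48 = 24
- Week 104: 104 − 72 = 32
- +24: 24
- +52: 52 − 24 = 28

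Follow-Up 1 varies with the date of the last dose. Under an assumed constant weekly probability h, the expected row value is 1 − (1 − h)^weeks:

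| h per week | 24 weeks | 28 weeks | 32 weeks |
|---|---|---|---|
| 0.05% | 1.19% | 1.39% | 1.59% |
| 0.10% | 2.37% | 2.76% | 3.15% |

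The ratio of 32 to 24 weeks is 1.59/1.19 = 1.34 and 3.15/2.37 = 1.33. The Week 104 row can therefore be about one third higher with no change in risk. The rows at Weeks 24, 48 and 72 have equal look-backs.

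**5. Is the patient-level count supplied elsewhere?** The outcome list in 1.1.2.4 and protocol 6.1.4 do not supply it. Section 5.7.2 counts patients with at least one occurrence, but only for adverse event preferred terms. Section 5.7.4 gives a proportion of patients with marked laboratory abnormalities during treatment. The plan uses patient-level counting elsewhere, but not for the C-SSRS.

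**The case against.** **Unscheduled visits may be included.** Section 5.7.7 refers to assessment visits without limiting them to scheduled ones, and no rule drops unscheduled records. Output layouts are also outside the SAP, so a shell could add an unscheduled row or a cumulative row. This stands in part: a reader might infer that the plan excludes these events, and the documents do not say so. The plan is silent, and loss is possible rather than stated. An unscheduled row would still not count patients once or mark findings as new.

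**Adverse event tables give a patient-level route.** Adverse events are sought at each contact (protocol 5.3.1), counted per patient and given as rates per patient-year (OLE SAP 5.7.2), and deaths are listed. This reduces the risk that a serious event goes unreported. However, no document requires a positive C-SSRS to be recorded as an adverse event.

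**The outcome is not worded as an incidence.** Section 1.1.2.4 uses that word for ARIA and adverse events but not for suicidality. That is correct, and the visit table is not in breach of the outcome list. It remains a weak summary of a safety outcome.

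**Recall may run from the last clinic visit.** With dosing every 4 weeks, the look-backs would then be similar and step 4 would largely disappear. But the Week 24 form would cover about 4 of the 24 weeks since the previous C-SSRS, so most of the interval would fall outside any scheduled form. The documents do not settle which reading applies.

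**Conclusion.** The point holds as a reporting gap that should be closed. The by-visit summary does not determine how many of the 230 OLE patients had any or new suicidality, and this needs no assumption about risk. Its size depends on the data: five positives in each of four rows would mean anything from 5 to 20 patients (2.2% to 8.7%). The lack of a rule for unscheduled forms rests on the SAP's silence. The difference of up to about one third between scheduled rows rests on recall running from the last C-SSRS and on constant risk.

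Two stronger readings are tempting but not supported:

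- **A steep artificial rise from Open-Label Day 1 to Week 24.** A reader might infer this because Part 1 treatment visits collected the C-SSRS every 4 weeks. No document gives a 4-week look-back at Day 1. The Part 1 SAP (4.1.5) expects some patients to start the OLE more than 28 days after their last double-blind dose, and Part 1 follow-up forms were at Weeks 116 and 152. The form used at Day 1 is not stated, Day 1 is a baseline row, and 5.7.7 plans no comparison of it with Week 24.
- **The same defect for ECGs.** Section 5.7.6 says "Abnormal ECG measurements will be summarized by previous randomization and overall at each assessment visit", but it also categorises QT/QTc outliers following E14. The listed outcome is worded in terms of abnormal assessments, and an ECG has no recall period.

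**What to change.** In OLE SAP 5.7.7, make a patient-level summary the main C-SSRS analysis:

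- Give the number and percentage of safety-evaluable patients with any ideation (worst category), any behaviour and any self-injurious behaviour without suicidal intent, by previous randomization and overall.
- Include every C-SSRS, scheduled or unscheduled, after the first OLE dose through the end of OLE follow-up, and count each patient once.
- Add a rate per patient-year whose denominator covers the same period. The denominator in 5.7.2 stops 4 weeks after the last dose and would not match.
- Show a shift from the worst pre-OLE category (lifetime baseline form plus double-blind forms) so that new findings are visible.
- State whether the recall period runs from the last C-SSRS or the last clinic visit.

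Keep the by-visit table as supportive. The cost is SAP wording and about one or two tables, all from data already collected.
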